5.3 Inclusion/Exclusion Criteria

See Table 4. With the exception of criteria relevant to SP inclusion (criteria 3, 4, 9, & 10), inclusion/exclusion criteria reflect those consistent with PE delivery within VA. RCT phase participants must meet diagnostic criteria for PTSD or subthreshold PTSD,⁹¹ assessed using the gold-standard Clinician-Administered PTSD Scale for DSM-5 (CAPS-5).³ Consistent with recommendations, subthreshold PTSD will be defined as endorsement of criteria A (trauma), F (duration), and G (impairment), with at least one symptom from each of the remaining diagnostic criteria.⁹² As IC phase participants' data NOT will be part of the larger RCT, how this is assessed for IC phase participants will vary to streamline recruitment processes. It will be assessed through a positive screen for PTSD on the PTSD Checklist (PCL-5)² administered in paper-and-pencil questionnaires. Items 5-7 will be assessed using the Clinical Trials Version of the Structured Clinical Interview for DSM-5 (SCID-5-CT)¹² for RCT participants. For IC phase participants, Items 5 and 7 will be assessed by self-report questionnaire (PHQ-9; AUDIT; DAST) and item 6 through hospital records review. Structured clinical interview for inclusion/exclusion criteria will be administered by trained and supervised assessors blinded to condition from the hub site (Minneapolis VA).

In order to finalize and solidify all processes before beginning the RCT phase of the study, Minneapolis assessors will administer the gold-standard Clinician-Administered PTSD Scale for DSM-5 (CAPS-5)³ and the Clinical Trials Version of the Structured Clinical Interview for DSM-5 (SCID-5-CT)¹² to up to ten Intensive Coaching (IC) cases. This process allows clinical interview administrators to acclimate to the interview procedures and to prepare for the RCT phase.

As all structured clinical interviews will be administered by Minneapolis VA staff, most interviews will take place by telephone. Minneapolis VA participants will have the option for in-person administration.

Table 4. Inclusion/exclusion criteria

Inclusions	Measure	Exclusions	Measure
1. Enrolled in VHA care	CPRS	6. Actively suicidal/homicidal with intent and/or plan in the last 30 days; hospitalized in the last 30 days for psychiatric reasons; multiple hospitalizations for psychiatric reasons in the past year	SCID-5-CT ¹²
2. Clinically significant PTSD symptoms	CAPS-5	7. Episode of mania/ psychosis in past 3 months	SCID-5-CT ¹²
3. Have a SP (intimate partner, family member, or friend) with contact at least 3 times a week	Self-report item	8. Severe substance use problem in past 3 months	SCID-5-CT ¹²
4. Will allow a SP to participate	Self-report item	9. Moderate relationship violence	IPSVS Adapted ¹⁰⁸
5. Willing to be seen via telehealth when in-person treatment options aren't available.		10. Veteran has underlying medical condition or a planned medical procedure likely to impair ability to engage in treatment.	
		11. SP screens positive for PTSD	PCL-5
		12. Veteran and/or SP fails to complete baseline survey	

Criteria for items 3-4 will be assessed through single yes/no self-report items administered to Veterans during telephone screens or on self-reports (IC participants only). Given the emphasis on flexibility, item 4 will require the Veteran to agree to (a) allow a SP to complete study assessments, (b) bring a SP to Session 1, if randomized to family supported PE, and (c) discuss further SP attendance with his/her provider. Variability in SP attendance will be included as a covariate in analyses and examined as a predictor of adherence. Relationship violence will be assessed by telephone from both Veteran and SP-report (item 9), defined as one or more episodes of severe violence in the past year (e.g., kicked or beat up) on the IPSVS Adapted Scale¹⁰⁶. We will exclude Veteran participants if he/she has an underlying medical condition or a medical procedure (item 10) planned that would greatly impair their ability to participate in a weekly psychotherapy (i.e., a severe seizure disorder making weekly attendance difficult or a planned major surgery within a month of beginning treatment). This item will be assessed during the initial phone screening. We will administer a PTSD screen (PCL-, response options adapted to a yes/no format for efficiency of delivery by telephone) to SPs by telephone and exclude SPs who screen positive for PTSD on the PCL-5. SPs and Veterans will be required to complete a baseline survey assessment before they can be randomized to a study arm. Failure to complete the baseline survey will result in study ineligibility (item 11). If a family member is determined to be ineligible due to a positive PTSD screen or failure to complete his/her baseline survey, but the Veteran is otherwise eligible, the Veteran will be contacted by telephone and given the opportunity to designate another family member for participation. The details of the reason their initial SP was ineligible will not be disclosed.

Regarding relationship violence, when the veteran reports they have been the target of moderate violence from their SP, the study team, under the supervision of the local Site PI, will determine if the violence should be the immediate focus of clinical attention. That is, (1) is the reporter is in danger of harm and, therefore, the focus of clinical attention should be on safety, or (2) would the reporter prefer to focus on IPV rather than PTSD. Importantly, each Site PI is a licensed, clinical psychologist with the appropriate training and expertise to make these

decisions. If the violence should be the focus of immediate clinical attention, then the dyad will be deemed ineligible and provided appropriate referrals. If the violence should not be the focus of clinical attention (e.g., the reporter is not in danger and does not wish to focus on IPV) the reporter may select a different loved one with which to participate in the study.

The new SP will also be screened and subject to the same inclusion/exclusion criteria, including that the new SP cannot be ineligible due to moderate IPV towards the veteran. The original SP will be deemed ineligible. The details of the reason the initial SP was ineligible will not be disclosed. The reporting dyad member(s) will be provided with resources and referrals for IPV (see IPV risk algorithm). Ineligible dyads may be re-evaluated for eligibility when this exclusionary criteria has been resolved (i.e., one year has passed without an episode of severe violence or six months without minor violence).

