Version date: August 26, 2020

Summary of revisions made: Amendment 15; added follow-up emails to provide participants with the online survey link and personal code, and revised follow-up letters to include survey URL and code.

Version number 16

Version date: September 7, 2021

Summary of revisions made: Amendment 16; adding information regarding teleform surveys being mailed from Atlanta site to main site in Mpls MN.

Abstract

Impacts. This study aims to improve Veterans' adherence to evidence-based treatment for PTSD, through increasing family support for treatment. Improving retention rates in evidence-based PTSD treatment will positively impact Veterans' health and well-being, lower the cost of treating PTSD, and decrease long-term demand for PTSD services. If effective, this approach could help resolve national calls for routine inclusion of family involvement in PTSD treatment. Once demonstrated for PTSD, these strategies could be utilized for other conditions and problems relevant to Veteran populations (e.g., suicide prevention, TBI rehabilitation) and stimulate shifts across practice and policy to better routine and evidence-based involvement of families in care.

Background. PTSD occurs in as many as 1 in 5 combat Veterans and is associated with a host of negative, long-term consequences to the individual, their families, and society at large. Evidence-based psychotherapies, such as Prolonged Exposure (PE), result in clinically significant symptom relief for many. Yet, adherence to these treatments (i.e., session attendance and homework compliance), which is vital to ensuring recovery, can be poor. Engaging families in Veterans' treatment may provide a powerful method for promoting EBP adherence. Our data indicate that 70% of Veterans express some interest in involving their family in their care for PTSD; yet, only 17% of providers have had any contact with Veterans' families. The objective of the proposed study is to evaluate the effectiveness of improving family support as a tool to improve Veterans' EBP adherence. This research agenda directly addresses two VA HSR&D priorities: 1) innovative mental health care; 2) improving the quality of life for Veterans and their caregivers. The work aligns with the VHA Blueprint for Excellence and Strategic Plan through meeting the unique needs of military-service disabled Veterans, providing a novel treatment approach, and emphasizing patient- and family-centered care.

Objectives/Aims.

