2.2 Strategies for Family Supported PE

2.2A. Structure of Standard PE.

The PE treatment protocol includes education, imaginal exposure (repeatedly imagining and describing a trauma memory to the provider), in vivo exposure homework (exposure to trauma reminders in real life), and listening to audio recordings of Veterans' trauma accounts between sessions (imaginal exposure homework).⁵² The first sessions are largely educational. Imaginal exposure begins in Session 3. Due to the volume of material provided in Session 2, in VA care, it is frequently divided into two sessions: 2a (education on PTSD and avoidance; detailed rationale for in vivo exposure) and 2b (building a hierarchy of situations to approach at home; see Figure 2).

2.2B. Overview of Family Supported PE.

SPs will attend PE Sessions 1, 2a, and 2b; receive two check-in telephone calls; and be invited to elective in-person check-ins if indicated (see below). Dividing Session 2 into 2a and 2b allows for more time to discuss the content outlined below. Strategies for how to engage with families are drawn from existing evidence-based approaches. The goals for family engagement are to 1) educate SPs about how avoidance maintains PTSD, 2) facilitate discussion of how SPs encourage/discourage PE participation (accommodation), and 3) develop a plan, tailored to the Veteran-SP dyad, for how SPs will help Veterans participate (support plans). The VHA Blueprint for Excellence emphasizes patient-centered care,⁴⁰ which is both flexible and tailored.⁴⁴ Flexibility is essential to implementation of family involved treatments,⁷⁶ and to improving the clinical relevance of interventions.¹⁴ Consequently, inclusion/exclusion criteria only require Veterans bring a SP to Session 1 (if randomized), and discuss further SP attendance with their provider.

2.2C. Description of Strategies.

[figure not shown]

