active-listening, and role plays, using BFT approaches. Lastly, it will use tips from Motivational Interviewing for eliciting SP encouragement for PE participation, creating a tailored plan for SPs to support PE, and assisting SPs in follow-up telephone calls. The training team is highly seasoned in educating providers in these methods. The training will be video-taped for use in training future providers (e.g., due to provider attrition during the course of the study).

5.1C. Standard PE.

Providers will deliver PE consistent with the standard of care, with a flexible end date as they typically would in routine practice and will divide Session 2 into 2a and 2b. VA PE trainings encourage extending the therapy as needed, routinely resulting in a range of 8 to 15 sessions. Posttreatment assessments will be scheduled to coincide with when Veterans complete treatment to allow for this flexible end date. If participants are still in treatment at 16 weeks post-session 1, the posttreatment assessment will be delayed to allow them to get through as much of the treatment as possible prior to assessment. If the Veteran never attends session 1, their posttreatment will be scheduled 16 post-first missed appointment for session 1.

Family attendance will not be solicited by providers in standard PE. If a SP contacts a provider, the provider will proceed as he/she would in his/her routine practice, consistent with our design emphasis on real-world care. Quantity and quality of provider-SP contact will be measured by weekly provider report. We anticipate risk for cross-over effects from SPs reaching out to providers is minimal as considerable effort is required by SPs to gain access to Veterans' providers (i.e., Veterans must request and sign a Release of Information). Additionally, while we did not capture who initiated the provider-SP contacts reported among 17% of SPs within Project HomeFront, qualitative interviews suggest these contacts are typically initiated by providers. In qualitative interviews, SPs were enthusiastic about being involved in Veterans' care, but few SPs had considered reaching out to Veterans' providers.

Table 2. Content Added for Family Supported PE	
PE#	Task
1	
 • Eliciting benefits of further SP attendance • Brief discussion of how SPs can help in PE
2a	
 • Brainstorm how SPs encourage/discourage PE adherence and approaching trauma-reminders

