2b	
 • Develop SP's plan for supporting adherence • Anticipate barriers to success; role play solutions
3, 5	
 • SP telephone check-ins for trouble-shooting support plan with longer in-person check-ins when indicated

5.1D. Family Supported PE (Table 2).

Providers will deliver the 10 session PE protocol as they typically would with additional material outlined session by session below. As discussed above, they will divide session 2 into 2a and 2b (11 total sessions delivered over an 11-16 week period). If the dyad is randomized to include their family in treatment sessions, SPs will attend the first session with the Veteran and be encouraged to attend both

session 2a and 2b (see Table 2). Each session attended by a family member will include the following content. We will ask Veterans in self-reports prior to session 1 about their preference for having their SP present for their Session 1 trauma discussion with their providers (i.e., trauma interview). This preference will be honored to promote early retention and keep the intervention Veteran-centered.

Session 1: The last twenty minutes of Session 1 will involve a) eliciting how further SP attendance could be of benefit the dyad, using Motivational Interviewing tips, b) discussion of how the SP can support PE participation should this be the only family session, c) and discussion of the benefits of talking further about trauma with loved ones, using Motivational Interviewing strategies.

Session 2a: We will devote fifteen minutes to discussing how SPs naturally encourage or discourage Veterans to approach trauma reminders and participate in treatment. Session 2b: Thirty minutes will be devoted to a) create a tailored plan for SPs to support Veterans' PE participation, including planning trauma disclosure to family when indicated or desired and b) problem-solving barriers to the success of the SPs' support plan.

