Telephone check-ins: Following Session 2b, SPs will have two 15 minute telephone check-ins to make support plan adjustments. Call 1 will occur after the first *in vivo* exposures (Session 3), and Call 2 will occur two weeks later. If telephone check-ins reveal a) the family support plan is not going well, b) unresolved ambivalence about the treatment, or c) requests for more assistance in supporting Veterans' care, providers can add dyadic session(s), consistent with how this intervention would likely be delivered in good clinical practice. These sessions will discuss progress and the support plan. They can also be used to plan and facilitate trauma

disclosure if clinically indicated and desirable. Dyads expressing additional family or SP needs (e.g. mental health), will be provided site-specific referrals, including services for SPs, children, parenting training, and family/couple counseling as indicated.

After finishing treatment in both study conditions, Veterans will be referred back to their VA mental health care team in order to determine if they have any remaining mental health treatment needs. If they do not already have an established primary mental health care team or provider, they will be referred to the mental health care team at their VA facility to establish care and evaluate any remaining mental health treatment needs.

5.1E. Delivery by Telemedicine

We will recruit participants from CBOCs and offer to provide Prolonged Exposure treatment within the study using telemedicine. The telemedicine option would use VA approved electronic communication methods and information technology to provide Prolonged Exposure therapy to patients by study clinicians. This option would greatly benefit participants. Psychotherapy, including Prolonged Exposure (PE), is currently widely available within VA by telemedicine to improve Veteran access to care. The major benefit of telemedicine is that it eliminates travel that may be disruptive or costly to patients. Many individuals in need of specialized PTSD services live in geographically remote regions. Additionally, individuals needing mental health services may have physical limitations or disabilities. Providing Prolonged Exposure therapy to these individuals solely in medical centers can impose a tremendous financial, travel, or personal burden. Allowing a telemental health option for PE therapy will ease these burdens by making services more accessible to patients.

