5.5A.6 Covariates. SP support for PE may better influence adherence with less SP distress, less family conflict, greater provider-SP contact, and certain demographic characteristics (e.g., gender, age, or race/ethnicity). SP distress will be assessed using the PROMIS Perceived Stress scale⁹⁸ and General Functioning scale of Family Assessment Device (FAD). Frequency of provider-SP contact will be assessed in weekly provider reports. Demographic variables such as race, gender, SP-Veteran relationship (e.g., spouse, parent, adult child), and frequency of SP-Veteran contact will also be assessed at Baseline.

5.5A.7 Qualtrics Online Surveys

Survey administration format will transition to Qualtrics FedRAMP electronic survey software accessed via the VA cloud. This transition will support data collection during the current COVID 19 directives. Our study sites have been ordered to "shelter in place" during the pandemic, making paper survey mailings unachievable. Paper surveys will still be available to those who need or request them, but we plan to use online surveys as our primary modality.

Qualtrics FedRAMP has been approved for use from the VA OIT Security standpoint (Authority to Operate or ATO). The ATO status is currently approved for 1 year and a full 3-year ATO is in the works. Qualtrics FedRAMP surveys will contain a study ID number, time of data entry and limited individually identifiable information. Within the VA firewall, the study team at the VA will create a custom- built tracking app that will track each participant's enrollment and study status. Data will be routinely extracted from Qualtrics FedRAMP in the VA cloud and stored on secure CCDOR servers, using SQL database connections. All data will be stored and utilized within secure CCDOR servers that are part of the Minneapolis VAMC network and which operate behind the VA firewall. All data is tracked using a SQL database, with a GUI-front end system that restricts access to only those with approval to study data.

Qualtrics FedRAMP surveys will contain minimal individually identifying information. The only identifying information will be information that is self-reported by the participants (e.g. name, phone, email, which is best method of contact). No sensitive data will be stored outside of the VA protected environment. Once data are transferred for data analysis, data will be maintained on password-protected VA computers in the VA environment and on secure VA servers.

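### Support-person attendance is capped by the Veteran's own attendance, so examining it as a predictor of sessions attended yields a positive association under no effect whenever some Veterans leave before Session 2b

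*Combined protocol and SAP*

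**What the plan says.** Section 5.3, in discussing how flexibly SPs may take part, says: "Variability in SP attendance will be included as a covariate in analyses and examined as a predictor of adherence". It does not define the measure (count, proportion or any attendance), the analysis set, or the time window of predictor and outcome.

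Section 2.2B describes the exposure: "SPs will attend PE Sessions 1, 2a, and 2b; receive two check-in telephone calls; and be invited to elective in-person check-ins if indicated". Section 5.1D is looser about the second and third sessions: "SPs will attend the first session with the Veteran and be encouraged to attend both" 2a and 2b. Later contact is possible: "Following Session 2b, SPs will have two 15 minute telephone check-ins to make support plan adjustments", and if these show difficulties "providers can add dyadic session(s), consistent with how this intervention would likely be delivered in good clinical practice". In the control arm, section 5.1C says "Family attendance will not be solicited by providers in standard PE".

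The Abstract defines the outcome side: "adherence to these treatments (i.e., session attendance and homework compliance), which is vital to ensuring recovery, can be poor". Section 5.6A makes session attendance the primary outcome. Section 5.6B2 models the number of sessions with treatment and site as fixed effects and provider as a random effect; SP attendance is not named there.

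**The concern.** An SP who joins the Veteran's session can be counted only if the Veteran comes. A Veteran who never starts scores 0 on SP attendance, one who stops after Session 1 scores at most 1, and only one who reaches 2b can score 3 from the three educational sessions. Early leavers are thus low on both variables by construction. This is a part-whole (immortal-time) dependence. It biases the association upwards, in the direction that favours family involvement.

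The trial is a Hybrid 1 design meant to inform implementation, and section 2.3 foresees follow-on work on how to implement family involvement. A result that more SP sessions go with more Veteran sessions could be read as dose-response evidence when part or all of it reflects who stayed in treatment.

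The same sentence also makes SP attendance a covariate without saying in which analyses. In a two-arm model it would be a post-randomisation variable that is essentially zero in one arm.

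**Working it through.** **Plan's own figure.** Section 5.6A1 gives mean 7.30 sessions, SD 4.45, a two-session difference, 80% power and 78 per arm. Assuming two-sided 5% (alpha is not stated), n per arm = 2 × (1.96 + 0.84)² × 4.45² / 2² = 77.7, so 78 is reproduced. The plan gives no figure for the SP-attendance analysis.

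**The cap.** Let V be Veteran sessions and S the number of Sessions 1, 2a and 2b with an SP present. Then S ≤ min(V, 3).

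**Inputs the documents do not give.** These are the share e leaving before 2b and the probability q that the SP is present at 2a or 2b when the Veteran is. The 35% drop-out in section 2.0 carries no timing. Section 5.1C does provide for Veterans who never attend Session 1.

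**One case by hand, SP effect exactly zero.** Take e = 10%, q = 0.7, SP always present at Session 1, leavers with 1 or 2 sessions equally often, others uniform on 3–15.

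- Mean V: leavers 1.5, stayers 9. Difference 7.5.
- Mean S: leavers 1 + 0.5 × 0.7 = 1.35, stayers 1 + 2 × 0.7 = 2.40. Difference 1.05.
- Cov(V,S) = 0.1 × 0.9 × 7.5 × 1.05 + 0.1 × (0.25 × 0.7) = 0.709 + 0.018 = 0.726. Among stayers the covariance is zero.
- Var(S) = 0.09 × 1.05² + 0.1 × (0.5 × 0.21 + 0.25 × 0.49) + 0.9 × (2 × 0.21) = 0.099 + 0.023 + 0.378 = 0.500.
- Var(V) = 0.09 × 7.5² + 0.1 × 0.25 + 0.9 × 14 = 5.06 + 0.03 + 12.60 = 17.69.
- Slope = 0.726 / 0.500 = 1.45 Veteran sessions per SP session; r = 0.726 / √(0.500 × 17.69) = 0.24.
- With n = 78, expected t ≈ 0.244 × √76 / √(1 − 0.244²) = 2.19, against a critical value of about 1.99, so a true null is rejected in about 58% of trials.

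Mean V here is 0.9 × 9 + 0.1 × 1.5 = 8.25, somewhat above the plan's 7.30.

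**Range by simulation** (n = 78, no SP effect, q = 0.5 to 0.9, leavers with 0–2 or 1–2 sessions):

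| Leave before 2b | False positives, V on S | Landmark at 2b |
|---|---|---|
| 0% | about 5% | 4–6% |
| 5% | 13–66% | 4–6% |
| 10% | 33–96% | 4–6% |
| 15% | 55–99% | 4–6% |
| 20% | 72–100% | 4–6% |

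These are approximate: a repeat of the 5% row gave 15–70%.

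**Matched to the plan's mean and SD.** A beta-binomial on 1–15 with mean 7.31 and SD 4.45 has 19% below three sessions. At q = 0.5, 0.7 and 0.9 it gives slopes of 1.67, 2.21 and 3.23, r of 0.27, 0.37 and 0.51, and rejection in 68%, 92% and 99.7% of trials. A beta-binomial on 3–15 has the same mean and SD, no early loss, and rejection of about 5%.

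**As a covariate across both arms.** With S = 0 throughout standard PE, least squares gives: treatment coefficient = (mean V in family arm − mean V in control) − slope × mean S in family arm. Under a true null the first term is zero on average. With the 1–15 distribution at q = 0.7, the simulated slope of 2.208 and coefficient of −4.837 imply a mean S of 4.837 / 2.208 = 2.19. Over q = 0.5 to 0.9 the coefficient runs from about −3.1 to −8.2 sessions and is significant in 58–99% of trials. With 10% early loss it is −2.4 to −6.0, with 5% it is −1.4 to −4.6, and with none it is about zero.

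**The case against.** The strongest reply is that the size is unknown and could be nil. That stands. A reader might infer that a strong, significant effect is certain; the documents do not support this. They do not say when the 35% drop out, and if every drop-out happened after 2b the test would behave normally, even at the plan's own mean and SD.

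A reader might also infer that the primary comparison is already compromised. Section 5.6B2 does not put SP attendance in the Aim 1 model, so that follows only if the covariate clause in 5.3 is carried into it.

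It is tempting to extend the defect to provider–SP contact. Section 5.5A.6 says "SP support for PE may better influence adherence with less SP distress, less family conflict, greater provider-SP contact", which lists contact among covariates or modifiers. It is reported weekly by providers, and section 5.1C measures it in standard PE too, so it is not simply a count of calls made after 2b.

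Adherence also includes homework compliance. The arithmetic cap applies to session counts; for homework it arises only if unassigned or missed homework is scored as non-compliance. Section 5.3 does not commit to a raw count either, though nothing in it rules one out.

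Finally, no passage says this analysis will drive a recommendation for more SP sessions; implementation findings come mainly from the Aim 3 process evaluation. That limits the consequence but leaves the analysis biased.

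**Conclusion.** The concern holds for session attendance. The planned predictor is bounded by the primary outcome, and nothing elsewhere in the documents removes the dependence. A positive association is expected under no effect whenever some Veterans leave before 2b. At 5% early loss the false-positive rate is already well above nominal (13–66%), and at 20% it is 72–100%. These figures assume 78 Veterans in the arm, SP presence at 2a and 2b of 50–90%, a count of SP-attended sessions as predictor, and a linear regression. Zero early loss would remove the problem, but the plan's provision for Veterans who never attend Session 1 makes that unlikely. A null simulation shows bias in the method; it does not show that SP attendance has no effect. The analysis is secondary, so this is a correction the plan should make and not a flaw in the primary test as written in 5.6B2.

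**What to change.** In sections 5.3 and 5.6B, replace the predictor clause with a specified analysis:

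- Exploratory and associational, within the family-supported arm only.
- Among Veterans who attended Session 2b, relate the number of Sessions 1, 2a and 2b with an SP present to the number of sessions attended after 2b.
- Alternatively, use SP presence to date as a time-varying predictor of attending the next session. This keeps Veterans who start and then leave early.
- For later dyadic sessions or check-in calls, count only exposure that precedes the outcome window.
- For homework compliance, state how missed sessions and unassigned homework are scored.

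Reconcile 5.3 with 5.6B2 by stating that SP attendance is not a covariate in the Aim 1 treatment-effect model, because it is post-randomisation and not solicited in standard PE.

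The cost is a few sentences and minor programming, with no new data collection and no change to the primary test. Veterans who stop before 2b do not contribute to the landmark version, so it says nothing about early retention. If SPs nearly always attend, there is too little variation to estimate anything. Confounding by the dyad's motivation remains in either version, hence the associational label.
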